ICH	International Council for Harmonisation
IgG	Immunoglobulin
ILD	Interstitial lung disease
imAE	Immune-mediated adverse event
IP	Investigational product
IO	Immuno-oncology
LLN	Lower limit of normal
mAb	Monoclonal antibody
MedDRA	Medical Dictionary for Regulatory Activities
NCI	National Cancer Institute
NE	Not evaluable
nmiss	No. of missing patients
no.	Number
NSCLC	Non-small-cell lung cancer
ORR	Objective response rate
OS	Overall survival
PD	Progressive disease
PFS	Progression-free survival
PCI	Prophylactic cranial irradiation
PK	Pharmacokinetic(s)
PLT	Platelet
PR	Partial response

Abbreviation or special term	Explanation
PT	Preferred term
q3w	Every 3 weeks
q4w	Every 4 weeks
QC	Quality control
RDI	Relative dose intensity
RECIST 1.1	Response Evaluation Criteria in Solid Tumors, version 1.1
SAE	Serious adverse event
SAP	Statistical analysis plan
SAS	Statistical analysis system
SBP	Systolic blood pressure
SCLC	Small-cell lung cancer
SD	Stable disease
SI	International system
SoC	Standard of care
SOC	System organ class
SS	Safety set
Std	Standard deviation
TBil	Total bilirubin
TC	Tumor cells
TFL	Table, figure and listing
TL	Target lesion
TSH	Thyroid-stimulating hormone
ULN	Upper limit of normal
WBC	White blood cell
WNL	Within normal limits

AMENDMENT HISTORY

Date	Category*: Change refers to	Description of change	In line with the CSP?	Rationale
2 Apr 2022	Other Page 2	Statisticians from Tigermed were added on signature pages. AZ statistician was changed from [name] to [name]. AZ medical advisor was changed from [name] to [name]. AZ global product statistician were added on signature page.	NA	Team member change in AZ. Tigermed SOP require signature of statistician from Tigermed for SAP.
2 Apr 2022	Other Section 2.2, page 13	4 general categories of IPD were deleted and replaced by the sentence ‘Several IPDs could be identified with programming to assist locating potential IPDs.’	Yes	The specification of IPD will be written in the external file of PD log but not in SAP.
2 Apr 2022	Derivation of primary or secondary endpoints Section 3.2.3, page 17	‘(2 x 6 weeks for tumor assessments + 2 x 2 weeks for permitted visit window)’ were added.	Yes	This sentence was added to explain clearly what the 2 visit after baseline means.
2 Apr 2022	Derivation of primary or secondary endpoints Section 3.2.3, page 18	In table 4, ‘Patients without PD and death’ was replaced by ‘Patients without PD and death but had post-treatment tumor assessment’.	Yes	To be more clear.
2 Apr 2022	Derivation of primary or secondary endpoints Section 3.2.3, page 18	In table 4, for the case of patient died after treatment without tumor assessment, 12 weeks was modified to 16 weeks.	Yes	Since 2 x 6 weeks for tumor assessments + 2 x 2 weeks for permitted visit window was defined for this case of censoring.
2 Apr 2022	Derivation of primary or secondary endpoints Section 3.2.4, page 19 Section 3.2.8, page 20	The sentence ‘which is the point estimate of PFS/ OS at the latest event \leq 365 day from first dose of study treatment’ were removed.	Yes	These sentences were used to specify the rules for programming. They could be written in ADaM specification instead of in SAP.
2 Apr 2022	Derivation of primary or secondary endpoints Section 3.2.5, page 19	It is emphasized that the denominator of ORR should be patients with measurable disease.	Yes	In CSP 2.0, inclusion criteria 8 was added to require that only patients with measurable disease at screening could be enrolled. And

2 Apr 2022	Derivation of primary or secondary endpoints Section 3.2.7, page 20	The domain of possible last recorded date that an individual patient was known to be alive was clearly stated.	Yes	the definition of ORR was modified accordingly.
2 Apr 2022	Other Section 3.3.1, page 21	[Redacted]	Yes	This clarification was to avoid ambiguous code in programming. The derivation rules were modified according to the data actually collected in EDC.
2 Apr 2022	Data presentations Section 3.3.2, page 22	The sentence 'Laboratory data will be from local laboratories and will be converted to AZ preferred units, and AZ project reference ranges will be used for the primary interpretation of laboratory data' was deleted.	Yes	AZ will not provide preferred units and reference ranges.
2 Apr 2022	Data presentations Section 3.3.8, page 23 and page 24	ALT and AST category added $>8x - \leq 10x$, $>10x - \leq 20x$. Sentence 'Plots of post-baseline ALT and AST vs. post-baseline total bilirubin will also be produced with reference lines at $3 \times \text{ULN}$ for ALT, AST, and	Yes	These categories were added to show more information. Plots of potential Hy's law case were not needed.

2 Apr 2022	Other Section 3.3.9, page 24 Section 4.2.3, page 28	2×ULN for Total bilirubin. In each plot, total bilirubin will be in the vertical axis' was deleted. Prior medication was defined as any medication that ended prior to the first dose of the study treatment	Yes	The definition of both prior and concomitant medication was deleted.
2 Apr 2022	Other Section 3.3.10, page 24	A new section about the definition of class of anti-cancer therapy was added.	Yes	To clearly distinguish previous, concurrent and subsequent anti-cancer therapy.
2 Apr 2022	Other Section 4.1.2, page 24	The sentence 'In addition, all efficacy and safety data and some selected relevant data (eg, patient disposition, demography and baseline characteristics) will be summarised separately for the WHO/ECOG PS 0 to 1 and 2 subgroups' was modified to 'In addition, some efficacy and safety data will be summarised separately for the WHO/ECOG PS 0 to 1 and 2 subgroups'.	Yes	Not all efficacy and safety data were needed to be analyzed for PS subgroup.
2 Apr 2022	Derivation of primary or secondary endpoints Section 4.1.6, page 26	In table 5 some derivation rules were added, including: time from original diagnosis to the first dose of study treatment, time from the latest assessment to the first dose of study treatment, time to first AE, and duration of AE.	Yes	These rules were added as needed.
2 Apr 2022	Derivation of primary or secondary endpoints Section 4.1.7, page 26	The sentence 'Imputation will be done only in the context of identifying treatment emergent adverse event (TEAE)' was deleted.	Yes	The imputation of date of AE will not only be used to identify TEAE, but also for other calculations, such as time to first AE.
2 Apr 2022	Data presentations Section 4.2.2.2, page 28	Variables of pathology of SCLC at screening include time from original diagnosis to the first dose of study treatment, time from the latest assessment date to the first dose of study treatment, pathology at diagnosis with primary tumor, regional lymph nodes and	Yes	This section was modified according to actual data collected.

		distant metastases TNM classification, and stage/AJCC stage.			
2 Apr 2022	Data presentations Section 4.2.2.4, page 28	It was added that ‘The event recorded in medical history page will be classified as medical history and current disease for summary. Any event that ended prior to the first dose of the study treatment will be considered as medical history. While those which ended after the first dose or are still ongoing will be considered as current disease’.	Yes	This sentence was added as demanded.	
2 Apr 2022	Data presentations Section 4.2.2.5, page 28	The methods, how concurrent anti-cancer therapy and subsequent anti-cancer therapy would be analyzed, were added.	Yes	This sentence was added as demanded.	
2 Apr 2022	Data presentations Section 4.2.2.6, page 28	The definition of concurrent and subsequent PCI was added.	Yes	This sentence was added as demanded.	
2 Apr 2022	Derivation of primary or secondary endpoints Section 4.2.4, page 29	Time to event will be censored at the date of DCO, death, 90 days after the last dose of durvalumab treatment or the date of initiation of the first subsequent therapy, whichever occurs first. K-M curve will be presented.	Yes	The rules of censoring was more clear and involve date of DCO into consideration. K-M curve was required.	
2 Apr 2022	Data presentations Section 4.2.5.4, page 30	DoR will be analysed in the same methods as PFS.	Yes	This sentence was modified to avoid unnecessary repeat.	
2 Apr 2022	Data presentations Section 4.2.6.1, page 30 and page 31	The information of summary of AE and death was modified.	Yes	The section was modified as demanded.	
2 Apr 2022	Data presentations Section 4.2.6.3, page 32	Shift tables for lab tests were added.	Yes	The section was modified as demanded.	

2 Apr 2022	Other Section 4.2.8, page 33	Definition of subgroups were modified.	Yes	The section was modified as demanded.
------------	---------------------------------	--	-----	---------------------------------------

* Pre-specified categories are
 Primary or secondary endpoints; Statistical analysis method for the primary or secondary endpoints; Derivation of primary or secondary endpoints; Multiple Testing Procedure; Data presentations; Other
 All the section and page no. in the second column corresponded to the location in SAP v1.0 which was finalized on 30 Oct 2020.

1 STUDY DETAILS

1.1 Study objectives

All objectives will be evaluated for all patients, unless otherwise indicated.

Primary objective:	Endpoint/variable:
To assess the safety and tolerability of durvalumab + EP in patients with performance status 0-2	Incidence of Grade ≥ 3 AEs Incidence of imAEs

AE Adverse event; EP Etoposide and platinum-based chemotherapy; imAE Immune-mediated adverse event.

Secondary objective:	Endpoint/variable:
To assess the efficacy of durvalumab + EP in patients with performance status 0-2	PFS, APF12, ORR, DoR using site Investigator assessment and OS, OS12
To further assess the safety and tolerability profile of durvalumab + EP	Incidence of AEs, SAEs, AESIs, AE resulting in treatment discontinuation

AESIs adverse events of special interest; DoR Duration of Response; EP Etoposide and platinum-based chemotherapy; ORR Objective response rate; OS Overall survival; OS12 Overall survival at 12 months after first dose of study treatment; PFS Progression free survival; APF12 Proportion of patients alive and progression free at 12 months after first dose of study treatment.

1.2 Study design

This will be an open-label, single-arm, multicenter, Phase IIIb study to determine the safety of durvalumab + etoposide and cisplatin or carboplatin as first-line treatment in patients with extensive stage small-cell lung cancer. Patients who fulfil all the inclusion criteria and none of the exclusion criteria will be enrolled and receive treatment with durvalumab + etoposide and either cisplatin or carboplatin (EP) for 4 to 6 cycles. Durvalumab will be administered at a dose of [REDACTED] every 3 weeks (Q3W) with first-line chemotherapy (EP) and will continue to be administered as monotherapy every 4 weeks (Q4W) post-chemotherapy until progressive disease (PD). Prophylactic cranial irradiation (PCI) is allowed at the investigators' discretion as per standard of care (SoC) guidance for extensive stage small-cell lung cancer (ES-SCLC). Patients will attend a safety follow up visit 90 days after last dose of durvalumab. The study flowchart is shown below in Figure 1 Overall study design.

Figure 1 Overall study design

ES-SCLC Extensive-stage small-cell lung cancer; EP etoposide + cisplatin or carboplatin; PD Progressive disease

The schedule of assessments including safety, tolerability, and efficacy using RECIST version 1.1 are detailed in the study assessment schedule in Appendix A.

Tumour assessments using computed tomography (CT)/magnetic resonance imaging (MRI) will be performed at the times specified in the schedule of assessment (Appendix A). RECIST 1.1 measurements as assessed by the Investigator will be used to derive the secondary variables of PFS, APF12, ORR, and DoR. The categorisation of objective tumour response assessment into complete response (CR), partial response (PR), stable disease (SD), progressive disease (PD) or not evaluable (NE) will be based on RECIST 1.1.

Patients will be followed for survival status every 3 months (q3m) following treatment discontinuation, until death, withdrawal of consent or the end of the study. These contacts may be conducted by phone and the survival data collected will be reported in the clinical database.

1.3 Number of patients

This is a safety study and no formal sample size calculation will be done. However, assuming AE of CTCAE grade ≥ 3 with an incidence of 60%, approximately 300 patients are needed to achieve the estimation precision no wider than 5.7% based on exact method (Clopper-Pearson). In addition, assuming the imAE with an incidence of 20%, the estimation precision will be no wider than 4.7% using the same method. An illustration of the precision around the varying incidences of AE for the patients enrolled is provided in Table 1 Precision around varying incidence of AE.

Table 1 Precision around varying incidence of AE

Sample Size	Precision achieved with different assumed incidence of AE				
	20%	40%	50%	60%	70%
200	5.8%	7.0%	7.1%	7.0%	6.6%
300	4.7%	5.7%	5.8%	5.7%	5.3%
500	3.6%	4.4%	4.5%	4.4%	4.1%

2 ANALYSIS SETS

2.1 Definition of analysis sets

2.1.1 Safety set (SS)

The safety analysis set will include all patients who received at least one dose of study treatment.

2.1.2 Efficacy analysis set

The safety set will be used as the efficacy analysis set.

2.2 Violations and deviations

Protocol deviations are defined as any change, divergence or departure from the study design or procedures defined in the protocol. Important protocol deviations (IPDs) are defined as a subset of protocol deviations that may significantly affect the completeness, accuracy, and/or reliability of the study data or that may significantly affect a patient's rights, safety, or well-being.

Categories of protocol deviations and IPDs will be documented by clinical operation team. Protocol deviations and IPDs will be recorded accordingly throughout the study by clinical investigators. Several IPDs could be identified with programming to assist locating potential IPDs.

These IPDs identified by programming will be reported to clinical operation team and be combined with clinical PD findings. The final combined PDs from clinical operation team will be used for statistical analyses.

A complete list of anticipated protocol deviations (including important protocol deviations) will be compiled separately and finalised prior to database lock.

3 PRIMARY AND SECONDARY VARIABLES

3.1 Primary endpoints

Primary endpoints include incidence of grade ≥ 3 AEs and incidence of imAEs.

Incidence of grade ≥ 3 AEs: Number and proportion of patients in SS with CTCAE (version 5.0) grade ≥ 3 AEs.

Incidence of imAEs: Number and proportion of patients in SS with imAEs.

imAEs: ImAEs will be identified from AEs of special interest (AESIs) based on programmatic rules that consider interventions involving systemic steroid therapy, immunosuppressant use, and/or endocrine therapy. Endocrine therapies include standard endocrine supplementation, as

well as treatment of symptoms resulting from endocrine disorders (for example, therapies for hyperthyroidism include beta blockers [e.g., propranolol], calcium channel blockers [e.g., verapamil, diltiazem], methimazole, propylthiouracil, and sodium perchlorate).

3.2 Secondary endpoints

Secondary endpoints include some variables regarding the efficacy of durvalumab + EP, such as PFS, APF12, ORR, DoR using site investigator assessment and OS, OS12 and some variables regarding the safety and tolerability of durvalumab + EP, such as incidence of AEs, SAEs, AESIs and AEs resulting in treatment discontinuation.

3.2.1 Derivation of RECIST visit responses

For all patients, the RECIST tumour response data will be used to determine each patient's visit response according to RECIST version 1.1. It will also be used to determine, if and when a patient's disease has progressed in accordance with RECIST and their best objective response to study treatment.

The baseline radiological tumour assessment is part of the screening procedure and should be performed no more than 28 days before the start of treatment, and ideally as close as possible to the start of study treatment. Tumour assessments will be at 6 weeks \pm 2 weeks after study treatment initiation, at 12 weeks \pm 2 weeks after study treatment initiation and then continue every 8 weeks \pm 2 weeks thereafter until disease progression. An additional follow-up scan will be performed if clinically feasible.

If an unscheduled assessment is performed, and the patient's disease has not progressed, every attempt should be made to perform the subsequent assessments at patients' scheduled visits. This schedule is to be followed to minimise any unintentional bias caused by some patients being assessed at a different frequency than other patients.

Additional scans can be completed per standard practice post-disease progression.

From the investigator's review of the imaging scans, the RECIST tumour response data will be used to determine each patient's visit response according to RECIST version 1.1. At each visit, patients will be programmatically assigned a RECIST 1.1 visit response of CR, PR, SD or PD, using the information from target lesions (TLs), non-target lesions (NTLs) and new lesions and depending on the status of their disease compared with baseline and previous assessments. If a patient has had a tumour assessment which cannot be evaluated, then the patient will be assigned a visit response of not evaluable (NE) (unless there is evidence of progression in which case the response will be assigned as PD).

RECIST outcomes (ie, PFS and ORR etc.) will be calculated programmatically from site investigator data from overall visit responses.

3.2.2 Site Investigator Assessments Using RECIST 1.1

Site investigator will record their assessment of overall response, and response in target lesions, non-target lesions, new lesions on the CRF form. Instructions to the investigator regarding selection of target and non-target lesions are included in Appendix C of the Clinical Study Protocol.

3.2.2.1 Target Lesions

Measurable disease is defined as having at least one measurable lesion, not previously irradiated, which is ≥ 10 mm in the longest diameter (LD), (except lymph nodes which must have short axis ≥ 15 mm) with CT or MRI and which is suitable for accurate repeated measurements.

All other measurable lesions not recorded as TL, and all non-measurable lesions (or sites of disease) should be identified as non-target lesions (NTLs) at baseline and their response should be followed at subsequent visits.

For patients who do not have measurable disease at entry (ie, no TLs) but have non-measurable disease, evaluation of overall visit responses will be based on the overall NTL assessment and the absence/presence of new lesions. If a patient does not have measurable disease at baseline, then the TL visit response will be not applicable (NA).

Missing TL Data

If all TL measurements are missing, then the TL visit response is NE. Overall visit response will also be NE, unless there is a progression of non-TLs or new lesions, in which case the response will be PD.

3.2.2.2 Non-Target Lesions and New Lesions.

At each visit an overall assessment of the NTL response should be recorded by the investigator. This section provides the definitions of the criteria used to determine and record overall response for NTL at the investigational site at each visit.

To achieve 'unequivocal progression' based on NTLs, there must be an overall level of substantial worsening in non-target disease such that, even in the presence of SD or PR in TLs, the overall tumor burden has increased sufficiently to merit a discontinuation of therapy. A modest 'increase' in the size of one or more NTLs is usually not sufficient to qualify for unequivocal progression status.

3.2.2.3 New Lesions

Details of any new lesions will also be recorded with the date of assessment. The presence of one or more new lesions is assessed as progression.

A lesion identified at a follow up assessment in an anatomical location that was not scanned at baseline is considered a new lesion and will indicate disease progression.

The finding of a new lesion should be unequivocal: ie, not attributable to differences in scanning technique, change in imaging modality or findings thought to represent something other than tumor.

New lesions will be identified via a Yes/No tick box. The absence and presence of new lesions at each visit should be listed alongside the TL and NTL visit responses.

A new lesion indicates progression, so the overall visit response will be PD irrespective of the TL and NTL response.

Symptomatic deterioration is not a descriptor for progression of NTLs: it is a reason for stopping study therapy and will not be included in any assessment of NTLs.

Patients with ‘symptomatic deterioration’ requiring discontinuation of treatment without objective evidence of disease progression at that time should continue to undergo tumor assessments where possible until objective disease progression is observed.

3.2.2.4 Overall Visit Response

Table 2 defines how the previously defined TL and NTL visit responses will be combined with new lesion information to give an overall visit response.

Table 2 Overall Visit Responses

Target	Non-target	New Lesions	Overall Visit Response
CR	CR (or NA)	No (or NE)	CR
CR	Non-CR/Non-PD or NE	No (or NE)	PR
PR	Non-PD or NE or NA	No (or NE)	PR
SD	Non-PD or NE or NA	No (or NE)	SD
PD	Any	Any	PD
Any	PD	Any	PD
Any	Any	Yes	PD
NE	Non-PD or NE or NA	No (or NE)	NE
NA	CR	No (or NE)	CR
NA	Non-CR/Non-PD	No (or NE)	SD
NA	NE	No (or NE)	NE
NA	NA	No (or NE)	NED

CR complete response; PR partial response; SD stable disease; PD progression of disease; NE not evaluable; NA not applicable (only relevant if there were neither target nor non-target lesions at baseline); NED no evidence of disease.

3.2.3 PFS

PFS is defined as the time from first dose of study treatment until the date of objective disease progression or death (by any cause in the absence of progression) regardless of whether the patient withdraws from study therapy or receives another anti-cancer therapy prior to progression. Patients who have not progressed or died at the time of analysis will be censored at the time of the latest date of tumor assessment. However, if the patient progresses or dies after 2 or more missed visits, the patient will be censored at the time of the latest assessment. If the patient has no evaluable visits or does not have baseline data, they will be censored at the day of first dose unless they die within 2 visits of baseline (2 x 6 weeks for tumor assessments + 2 x 2 weeks for permitted visit window).

The PFS time will always be derived based on assessment dates not visit dates.

$PFS \text{ (months)} = (\text{Date of event or censoring} - \text{Date of first dose} + 1) / 30.4375$, results round to 1 decimal place. The cases of event and censoring are listed in Table 4 PFS calculation under various cases.

Given the scheduled visit assessment scheme (ie, q6w ± 2w for the first 12 weeks then q8w ± 2w thereafter) the definition of 2 missed visits will change. To evaluate the no. of missing tumor assessments between the first PD/death and the last non-missing tumor assessment before, following rules will be used.

Table 3 Criteria of at least 2 missing tumor assessments

Cases	Conditions when considered as at least 2 missing tumor assessments
There is 2 consecutive missed tumor assessments before first PD/death since first dose.	Time interval between first dose and first PD/death is >16 weeks (ie. 2 * 6 + 4 weeks, 112 days)
If the 2 consecutive missed tumor assessments occur over the period(Week 12) when the scheduled assessments changes from q6w to q8w	Time interval between the last tumor assessment and first PD/death is >18 weeks (ie. 6 + 8 + 4 weeks, 126 days)
If the 2 consecutive missed tumor assessments occur after Week 12 onwards	Time interval between the last tumor assessment and first PD/death is >20 weeks (ie. 2 * 8 + 4 weeks, 140 days)

Table 4 PFS calculation under various cases

Cases	Date used as the end of PFS	Event or Censoring
Patients with PD or death, and first PD or death are within 2 assessments after last tumor assessment before PD/death	Date of first PD or death	Event
Patients with PD or death, and first PD or death are after 2 or more missing assessments from last tumor assessment before PD/death	Date of the last non-PD tumor assessment after first dose	Censoring

Patients without PD and death but had post-treatment tumor assessment	Latest date of tumor assessment after first dose	Censoring
Patient is alive and has no tumor assessments after first dose or does not have baseline tumor data	Date of first dose	Censoring
Patient has died >16 weeks after start of treatment and has no tumor assessments after first dose or does not have baseline tumor data	Date of first dose	Censoring

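### PFS and APF12: the text and Table 4 of SAP 3.2.3 disagree for patients with only not-evaluable scans, and Table 4 gives no date for progression first seen after two missed scans

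*SAP*

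**What the plan says.** SAP 3.2.3 gives the rules in running text and then in Tables 3 and 4.

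- **Text, no usable scan:** "If the patient has no evaluable visits or does not have baseline data, they will be censored at the day of first dose", qualified by "unless they die within 2 visits of baseline (2 x 6 weeks for tumor assessments + 2 x 2 weeks for permitted visit window".
- **Text, no PD and no death:** "Patients who have not progressed or died at the time of analysis will be censored at the time of the latest date of tumor assessment".
- **Text, event after a gap:** "if the patient progresses or dies after 2 or more missed visits, the patient will be censored at the time of the latest assessment".
- **Table 3** turns two missed assessments into time limits: more than 112 days from first dose if there was no earlier scan, more than 126 days from the last scan if the gap spans Week 12, and more than 140 days after that.
- **Table 4, row 1** counts PD or death within those limits as an event.
- **Table 4, row 2** censors PD or death beyond them at "Date of the last non-PD tumor assessment after first dose".
- **Table 4, row 3** censors patients without PD or death at "Latest date of tumor assessment after first dose".
- **Table 4, row 4** censors at first dose, and its condition is "Patient is alive and has no tumor assessments after first dose or does not have baseline tumor data". Row 5 does the same for deaths after 16 weeks.

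SAP 3.2.1 settles what an unreadable scan is, setting aside those that show progression and count as PD: "If a patient has had a tumour assessment which cannot be evaluated, then the patient will be assigned a visit response of not evaluable (NE". It is an assessment, but not an evaluable one.

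**The concern.** The text ties first-dose censoring to evaluability, and Table 4 ties it to whether any scan was done. The two conditions separate for a patient whose only post-baseline scans are NE, and both event status and PFS time can then change.

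The second problem is a gap. Table 4 row 2 assumes that at least one non-PD scan followed first dose. A patient who misses the first two scans and then shows PD on the first scan obtained meets the row 2 condition but has no such date.

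PFS and APF12 (the Kaplan-Meier estimate at 12 months, SAP 3.2.4) both use these rules. If the choice is left until programming, it may be made after data have been seen, in an open-label, single-arm study with investigator-assessed progression.

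**Working it through.** **Inputs.** Scans at Weeks 6 and 12, then every 8 weeks, each ±2 weeks (SAP 3.2.1). PFS in months = (end date − first dose date + 1) / 30.4375 (SAP 3.2.3). Below, Week w is taken as 7w days after first dose.

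**The plan's own limits reproduce.** (2×6+4)×7 = 112 days, (6+8+4)×7 = 126 days and (2×8+4)×7 = 140 days. The 16-week limit is the same in the text, Table 3 row 1 and Table 4 row 5.

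**Fault 1: only NE scans, at Weeks 6 and 12 (days 42 and 84).**

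| Patient | By the text | By Table 4 |
|---|---|---|
| Alive | No evaluable visit: censored at first dose, (0+1)/30.4375 = 0.03, i.e. 0.0 months | Row 3: censored at Week 12, (84+1)/30.4375 = 2.79, i.e. 2.8 months |
| Dies at Week 20 (day 140) | 140 > 112, so the exception fails: censored at first dose, 0.0 months | Row 1: 140 − 84 = 56 days since the last scan, inside the 140-day limit: event at (140+1)/30.4375 = 4.63, i.e. 4.6 months |

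With a single NE scan at Week 6 and the patient alive, the results are 0.0 months against (42+1)/30.4375 = 1.41, i.e. 1.4 months.

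**Fault 2: Weeks 6 and 12 missed, first scan at Week 20 shows PD; baseline data present.**

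1. 140 > 112 days, so Table 3 row 1 counts two missed assessments and Table 4 row 1 is excluded.
2. Table 4 row 2 applies, but there is no non-PD scan after first dose to supply the date.
3. Row 3 fails because there is PD. Row 4 fails because there is a post-dose scan and baseline data. Row 5 fails for the same reason and also requires death.
4. The text's first-dose rule fails too, because a PD visit is evaluable. Its rule for events after missed visits points to the latest assessment. If that is the baseline scan (1 to 28 days before first dose), PFS runs from (−28+1)/30.4375 = −0.9 to (−1+1)/30.4375 = 0.0 months. If it is the PD scan itself, PFS is 4.6 months.

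**Controls, where text and table agree.** No scans and death at Week 10 (70 ≤ 112 days): event at 71/30.4375 = 2.3 months in both. No scans and death at Week 20: first-dose censoring in both. PD on a first scan at Week 15 (105 ≤ 112 days): event at 106/30.4375 = 3.5 months in both. The faults are confined to the situations described.

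**Where the two faults meet.** With NE at Week 6 and PD at Week 20, the gap from the NE scan is 140 − 42 = 98 days, inside 126. If NE counts as an assessment, this is an event at 4.6 months. If NE counts as missing, the patient falls into fault 2.

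**Numbers affected.** The SAP gives none. Assuming 1% to 5% of the 300 patients in SAP 1.3: 0.01×300 = 3 to 0.05×300 = 15.

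**The case against.** The strongest reply is that the situations are uncommon, PFS and APF12 are secondary, and no test, error rate or sample size depends on them. The ADaM specifications are separate documents and may already resolve both points. This stands as a limit on importance, and it rules out saying that programming will be inconsistent. It does not cure a mismatch inside the SAP.

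A reader might also infer more than the SAP supports:

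- *That one patient could be an event, a Day 1 censoring or undefined.* No single patient gets all three on a literal reading. Event against Day 1 arises for NE-only patients who die after Week 16; the missing date arises for PD on a first scan after Week 16.
- *That censoring at an NE scan, or counting gaps from one, is itself a contradiction.* The text's general censoring rule and Table 4 row 3 agree on any tumour assessment. An NE scan can then extend follow-up and restart the missed-visit clock although it cannot exclude progression. Using evaluable scans instead would be an improvement, not the correction of an inconsistency.
- *That DoR is affected throughout.* DoR is calculated only for responders (SAP 3.2.6). NE-only patients and patients with PD on their first scan have no response, so only the NE follow-up and clock rule reaches DoR.
- *That the rules favour the treatment.* The direction is mixed. An NE scan lengthens censored follow-up, but restarting the clock also keeps later deaths and progressions as events.

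**Conclusion.** Two derivation faults in SAP 3.2.3 hold for PFS and APF12. For NE-only patients the text and Table 4 give different times, and for deaths after Week 16 they can also give different event status. For PD on a first post-dose scan more than 16 weeks after first dose, Table 4 supplies no date. Both follow from the SAP's wording together with its treatment of NE scans in 3.2.1; no outside assumption is needed.

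The count of 3 to 15 patients rests entirely on the assumed 1% to 5%. No effect on the median or on APF12 was computed; at such counts the effect on median PFS is probably small. Severity: minor.

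**What to change.** In SAP 3.2.3 and Tables 3 and 4:

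1. Use *evaluable tumour assessment* throughout, for both the censoring date and the counting of gaps. SAP 3.2.5 already refers to the last evaluable assessment for ORR, so the term is not new. This also stops an NE scan from extending follow-up or restarting the clock.
2. State one rule for patients with no evaluable post-baseline scan: death within 16 weeks of first dose is an event; otherwise censor at first dose.
3. Add to Table 4 row 2: *if none, date of first dose*. This matches rows 4 and 5.

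The cost is SAP wording and the matching ADaM derivation, with no new data and no change in sample size. There is a statistical price: a few late deaths or progressions after NE-only scans, such as the Week 20 cases above, become first-dose censorings instead of events. The choice should therefore be made and recorded before database lock.
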